2 INTRODUCTION

2.1 Trial rationale

For early stage, non-metastatic PDAC, complete surgical resection can result in cure for some patients. mFOLFIRINOX is currently adapted as an adjuvant therapy for resectable PDAC, however, relapse in this setting is common, with a 3-year disease-free survival (DFS) realized in less than 40% of patients (Conroy et al. 2018). Improved PDAC adjuvant treatment options are therefore a high priority for clinical development.

BNT321-02 is planned as a Phase I/II clinical trial to evaluate the safety, multicycle tolerability, and efficacy of mFOLFIRINOX ± BNT321 as a novel combination adjuvant therapy for patients with R0 or R1 resected PDAC. The Phase I part of this trial will determine the safety and BNT321 recommended Phase II dose (RP2D) together with chemotherapy for previously untreated patients who are eligible to receive 24 weeks of PDAC adjuvant therapy. A key secondary pharmacodynamic endpoint in Phase I is determining the extent of complement-dependent cytotoxicity (CDC) and antibody-dependent cellular cytotoxicity (ADCC) effects in peripheral blood longitudinally over an extended adjuvant therapy course. The safety and feasibility of continuing BNT321 monotherapy for 24 weeks beyond the initial 24 weeks of combination treatment will also be determined.

The BNT321-02 randomized Phase II part of this trial is a dedicated evaluation of the potential for mFOLFIRINOX + BNT321 combination therapy to provide meaningful clinical benefit over standard adjuvant mFOLFIRINOX. The Phase II part is designed to detect a substantial increase in median disease-free survival (mDFS), specifically with a target 36 months mDFS which represents more than 12 months improvement over current chemotherapy. Overall survival (OS) is a secondary endpoint for the Phase II, and demonstrated improvements will provide additional evidence of clinical benefit and further support the performance of additional follow-on trials in PDAC. Additional evaluations are limited pharmacokinetic and pharmacodynamic (ADCC, CDC, circulating tumor DNA [ctDNA], and CA19-9) assessments, which may help further characterize the clinical benefit and allow for more tailored designs in follow-on BNT321 trials.

For a rationale for the trial design, see Section 4.2.

For the rationale for the dosing regimen, see Section 6.2.

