4.1.4 Duration of the trial periods

For both Phase I and Phase II, there will be a screening period of 21 days.

Phase I will consist of ~48 weeks of therapy, with 24 weeks of mFOLFIRINOX + BNT321 combination therapy followed by 24 weeks of BNT321 monotherapy. Phase II will be a randomized 2-arm trial, with 48 weeks of treatment in the combination arm (mFOLFIRINOX + BNT321) and 24 weeks of therapy in the control arm (mFOLFIRINOX only).

For both Phase I and Phase II, there will be a safety follow-up of 2 days \pm 14 days after the last dose of trial treatment. DFS status will be recorded every 3 months for 2 years and then every 6 months for the next 3 years. Overall survival status will be recorded up to 60 months.

The maximum trial duration for each phase is ~5 years after the last patient's first treatment in the trial.

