Another key element of the BNT321-02 Phase I design is an extended monotherapy antibody treatment course beyond the initial 24 weeks in mFOLFIRINOX combination. The trial design is for single agent BNT321 administered on every 2 week schedule for an additional 24 weeks to complete a 48 week total adjuvant treatment course. The large majority of PDAC disease relapse occurs beyond the initial 6 months post-operative period when mFOLFIRINOX is administered. Extending the total treatment duration may further enhance the overall efficacy of adjuvant therapy in these patients. The approach of extended antibody monotherapy after an initial cytotoxic regimen has been successfully adopted in other adjuvant regimens, for example breast cancer adjuvant Trastuzumab

Page 47 of 127 Version: 2.0 Date: 22 JAN 2024

(Slamon et al. 2011). Extended BNT321 monotherapy will be adopted for the Phase II design following safety and tolerability confirmation from Phase I.

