9.5.4 Analysis of safety data

Safety data that will be summarized includes AEs, clinical laboratory parameters, vital signs, and ECGs. All safety analyses will be based on the Safety Analysis Set and will be summarized descriptively by treatment group Phase II/cohort Phase I unless otherwise stated.

Adverse events

AEs will be coded using the most recent version of Medical Dictionary for Regulatory Activities (MedDRA®) coding system to get a System Organ Class (SOC) and Preferred Term (PT) for each AE and graded for severity using NCI CTCAE v5.0.

A treatment-emergent AE is defined as any AE with an onset date on or after the first administration of IMP (if the AE was absent before the first administration of IMP) or worsened after the first administration of IMP (if the AE was present before the first administration of IMP). AEs with an onset date more than 28 days after the last administration of IMP will be considered as treatment-emergent only if assessed as related to IMP by the investigator.

Treatment-emergent AEs (as defined in Section 10.4.1) will be summarized overall and by treatment group Phase II/cohort Phase I.

The number and percentage of patients reporting at least one AE will be summarized by PT nested within SOC for each of the following AE types:

- Any AE
- Related AE
- Grade ≥3 AE
- Related Grade ≥3 AE
- Any SAE
- Related SAE
- · SAE leading to death
- AEs leading to dose reduction
- AE leading to permanent discontinuation of treatment
- DLT (Phase I only)
- AESIs

Moreover, the number and percentage of patients with any AE will be summarized by worst NCI CTCAE grade by PT nested within SOC.

For Phase I only, DLTs will be presented in terms of listings presenting the reported term and MedDRA PT and SOC term, its time of onset, duration, and outcome, relationship, NCI CTCAE grade, and seriousness including dose exposure data.

Page 93 of 127 Version: 2.0 Date: 22 JAN 2024

Laboratory parameters

Clinical laboratory assessments to be summarized include hematology, blood chemistry, and urinalysis. The clinical laboratory parameters to be assessed are listed in Section 8.3.4 and at the time points specified in the SoA (Section 1.3).

Clinical laboratory parameters at each timepoint and change from baseline to each postbaseline timepoint will be summarized using descriptive summary statistics for each parameter by treatment group Phase II/cohort Phase I.

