Clinical laboratory results will be classified according to the most recent version of NCI CTCAE. Shift tables from baseline to worst grade on-treatment will be provided for each laboratory parameter by treatment group Phase II/cohort Phase I.

Additionally, the occurrence of clinically significant abnormal laboratory results within a patient will be analyzed using descriptive summary statistics for each parameter and visit by treatment group Phase II/cohort Phase I.

Laboratory results will be listed along with the normal ranges and NCI CTCAE grade. Laboratory values that are below or above the normal ranges will be flagged.

Vital signs

Vital sign parameters to be assessed are listed in Section 8.3.2 and at the time points specified in the SoA (Section 1.3).

Vital sign parameters at each timepoint and change from baseline to each post-baseline timepoint will be summarized using descriptive summary statistics for each parameter by treatment group Phase II/cohort Phase I.

Additionally, the occurrence of abnormal vital sign results within a patient will be analyzed using descriptive summary statistics for each parameter and visit by treatment group Phase II/cohort Phase I.

ECG

ECG parameters to be assessed are listed in Section 8.3.3 and at the time points specified in the SoA (Section 1.3).

ECGs will be judged by the investigator as clinically significant (yes/no). The number and percentage of patients with clinically significant ECG findings will be summarized by treatment group Phase II/cohort Phase I for each visit.

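### Section 9.5.4 plans no adverse-event or worst-grade table for the BNT321 monotherapy period, although the trial is to determine that period's safety and feasibility

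*Combined protocol and SAP*

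**What the plan says.** **The question the trial sets itself.** Section 4.1.4 describes the Phase I course as "24 weeks of mFOLFIRINOX + BNT321 combination therapy followed by 24 weeks of BNT321 monotherapy". Section 2.1, repeated in the synopsis, states: "The safety and feasibility of continuing BNT321 monotherapy for 24 weeks beyond the initial 24 weeks of combination treatment will also be determined". Section 4.2.1 attaches a consequence: "Extended BNT321 monotherapy will be adopted for the Phase II design following safety and tolerability confirmation from Phase I". Section 6.2 likewise introduces the 48-week regimen in Phase II after safety and dose determination in Phase I.

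**The planned tables.** Under Section 9.5.4, safety data "will be summarized descriptively by treatment group Phase II/cohort Phase I unless otherwise stated". For AEs:
- Treatment-emergent events are tabulated in total and per arm or cohort.
- Incidence is a count of patients: "The number and percentage of patients reporting at least one AE will be summarized by PT nested within SOC", with one such table per listed AE type.
- In addition, "the number and percentage of patients with any AE will be summarized by worst NCI CTCAE grade by PT nested within SOC".

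For laboratory data, "Shift tables from baseline to worst grade on-treatment will be provided for each laboratory parameter", again by arm or cohort. The analysis set is the Safety Analysis Set, which Section 9.4 defines as everyone with at least one IMP dose. The Phase I primary safety summaries in Section 9.5.2 use the same set and the same at-least-one-event counting.

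**What is planned by time.** Section 9.5.4 does summarize laboratory values and vital signs at each timepoint. Clinically significant laboratory abnormalities, abnormal vital signs and clinically significant ECG findings are summarized by visit.

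**The concern.** Monotherapy follows 12 cycles of a toxic chemotherapy regimen. A table that counts each patient once over the whole course, from a pre-treatment baseline, mixes the two periods. Three things are lost:
- **Recurrence.** A patient with an event in Cycle 3 and the same preferred term again in Cycle 15 adds nothing to that row the second time. The same holds for an any-event row such as any Grade ≥3 AE. A different preferred term gets its own row, but the row does not show when it occurred.
- **Worst grade.** If the worst grade was reached on chemotherapy, a later and smaller worsening on BNT321 alone does not appear in the shift table.
- **Denominator.** Patients who stop before Cycle 13 stay in the denominator although they were never at risk of a monotherapy event.

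At stake is whether the planned Phase I output can answer the question in Section 2.1 and support the step in Section 4.2.1. In Phase II, the arms receive 48 and 24 weeks of treatment, so whole-course AE percentages also compare periods of unequal length.

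**Working it through.** The plan states no figure here, so there is nothing to reproduce. The check has two parts: which outputs cover Cycles 13–24, and how much a pooled count could conceal.

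**1. Outputs set against the monotherapy question**

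| Output | Shows Cycles 13–24 separately? |
|---|---|
| Dose-limiting toxicities (6.3.2) | No; the window is the first two BNT321 doses, Cycles 2–3 |
| AE incidence, all types (9.5.2, 9.5.4) | No |
| AE worst grade (9.5.4) | No |
| AESIs (8.4.8, 9.5.4) | No, though the AESI definitions in 8.4.8 require relation to BNT321 |
| Laboratory shift to worst grade (9.5.4) | No |
| Laboratory and vital signs by timepoint; laboratory, vital-sign and ECG abnormalities by visit (9.5.4) | Yes |
| Exposure (9.5.6) | By drug, not by period; no count starting or completing monotherapy |
| Main quality-of-life comparison (9.5.3) | No; it is at the end of Cycle 12 |

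Section 10.4.3 has the investigator relate each event to BNT321 or mFOLFIRINOX, but Section 9.5.4 does not split the related-AE tables by drug.

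**2. Illustration of the pooled count**

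Inputs are any-grade rates from the earlier Phase I trial, as quoted in Section 2.3.2 and Table 5: *c* for mFOLFIRINOX + BNT321 (15 patients) and *m* for BNT321 alone. Phase I has about 20 patients.

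Pooled rate = *c* + (1 − *c*) × *m*, assuming independent periods and that all 20 patients reach monotherapy. For nausea: 0.867 + 0.133 × 0.256 = 0.901.

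| Event | *c* | *m* | Affected in monotherapy (20*m*) | Added to pooled count (20(1−*c*)*m*) | Pooled rate | Range, full to no overlap |
|---|---|---|---|---|---|---|
| Nausea | 86.7% | 25.6% | 5.1 | 0.7 | 90.1% | 86.7–100% |
| AST increased | 53.3% | 39.0% | 7.8 | 3.6 | 71.5% | 53.3–92.3% |
| ALT increased | 46.7% | 42.7% | 8.5 | 4.6 | 69.5% | 46.7–89.4% |
| Infusion reaction | 20.0% | 17.1% | 3.4 | 2.7 | 33.7% | 20.0–37.1% |

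Under independence, the share of monotherapy-affected patients who add nothing to the row equals *c*: 87%, 53%, 47% and 20%. Concealment is thus heavy for common chemotherapy effects and light for rarer ones.

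If only 70% (14 of 20) reach monotherapy, replace *m* by 0.7*m*. AST becomes 0.533 + 0.467 × 0.273 = 66.0%, which adds 2.5 patients. ALT becomes 0.467 + 0.533 × 0.299 = 62.6%, which adds 3.2.

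The most saturated row is any Grade 3–4 AE, at 75.9% on mFOLFIRINOX alone (Section 2.2.1). With 14 of 20 entering and an assumed 20% rate in monotherapy, the pooled figure is 1 − 0.241 × (1 − 0.14) = 79.3%, or 0.7 of a patient. At an assumed 40% it is 1 − 0.241 × (1 − 0.28) = 82.6%, or 1.3 patients. A period table would show 2.8 and 5.6 of 14.

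**3. Denominator.** Three affected patients are 3/14 = 21.4% of those at risk in that example, but 3/20 = 15.0% of the Safety Analysis Set.

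**The case against.** A reader might infer that monotherapy toxicity is hidden altogether and that Phase II would adopt monotherapy on figures driven by chemotherapy. The documents do not support that.
- **Liver tests can be followed.** They are the first-listed BNT321 risk in Table 5. The by-timepoint and by-visit laboratory summaries, and the listings with CTCAE grade, show ALT, AST and bilirubin in Cycles 13–24.
- **AESIs are tied to BNT321.** Section 8.4.8 restricts them to BNT321-related infusion reactions and liver findings, so that table is not simply a chemotherapy table.
- **The decision need not rest on the tables.** Section 10.1.5 has the safety review committee review data by patient, by cohort and cumulatively, and no section names the 9.5.4 tables as the basis for the 4.2.1 confirmation. With about 20 patients, onset dates show the period directly.
- **More detail is to come.** Section 9.5 calls itself a summary and defers detail to a SAP, whose detailed text is not part of what is supplied. A by-period table cannot be shown to be absent from it. Nor does Section 3 list monotherapy safety as a separate objective.
- **Precision is low.** 3 of 14 has an exact 95% interval of about 5% to 51%.

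All of this stands, and it narrows the point without removing it. The by-visit tables do not cover AEs: infusion reactions, gastrointestinal events, SAEs, dose reductions and AE-driven discontinuation. They give status at a visit, not the proportion of monotherapy patients whose grade worsened. The committee's stated cuts do not include treatment period. Section 9.5 requires the SAP only before the first database lock for the primary analysis. If that means the DFS analysis at about 164 events, it comes after monotherapy has been adopted. Low precision is a reason to show counts, not to pool.

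**Conclusion.** The point holds in a limited form. Followed as written, Section 9.5.4 yields no monotherapy AE rate, no monotherapy AE worst grade and no worst-grade laboratory shift within monotherapy, and none of these tables uses patients entering monotherapy as its denominator. This follows from the grouping rule; no sentence announces that the periods will be pooled.

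The size depends on the event. Under the illustration, between 20% (infusion reaction) and 87% (nausea) of patients affected in monotherapy would leave the corresponding row unchanged, and those who do add to it could not be placed in a period. These figures assume independent periods and rates carried over from an earlier trial in advanced disease; the overlap range is wide. They show the mechanism and do not predict this trial's results.

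The primary DFS analysis is unaffected. The change is worth making because the trial names the question and ties a design step to its answer.

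**What to change.** In Section 9.5.4, add AE incidence, AE worst-grade and laboratory-shift tables by treatment period, for Phase I cohorts and for Phase II:
1. **Period 1:** first dose up to the start of BNT321 monotherapy. For the control arm, use its full treatment period, which gives a like-for-like comparison of the arms.
2. **Period 2:** first monotherapy dose to the end of the TEAE window, with patients who received at least one monotherapy dose as denominator.

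Count AEs that start or worsen within the period. Give laboratory shifts from the last value before the first monotherapy dose to the worst grade in Period 2.

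Two definitions need settling. Section 6.3.1.1 allows BNT321 to continue alone when chemotherapy is delayed or stopped for a chemotherapy-related AE, which can happen before Cycle 13; state to which period that exposure belongs. The TEAE window is 28 days in Section 9.5.4 but 60 days in Section 10.4.1, so those passages must be reconciled before Period 2 has a defined end.

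For feasibility, report the numbers starting and completing the 12 monotherapy cycles, with reasons for stopping. Provide the Phase I output to the safety review committee to support the confirmation in Section 4.2.1.

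The cost is some wording and a few repeated tables from data already collected. Phase I denominators will be small, so show counts beside percentages.

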- 19. ECGs will be performed at screening and on Day 1 of every cycle for C1 through C3. On these days ECGs are obtained prior to treatment, at t_{max}, and at end of last mFOLFIRINOX infusion. Investigators may obtain ECGs at additional timepoints in Cycle 4 to 12 if indicated based on results in Cycle 1 to 3. ECGs will also be obtained prior to first BNT321 administration on Cycle 13, and at EOT and as clinically indicated during BNT321 monotherapy per assessment of the trial investigator. ECGs are performed as triplicate exams at all study timepoints per Section 8.3.3.

Clinical Trial Protocol BNT321-02

Page 13 of 127

Version: 2.0

BNT321-02

Date: 22 JAN 2024

- 20. Complete blood count (CBC) with differential to include WBC, RBC, HGB, HCT, platelets, MCV, and MCH to be performed at screening and for every cycle on Day 1 and Day 8 until EOT and at safety FU visit.
- 21. Blood chemistry to include sodium, potassium, chloride, bicarbonate, blood urea nitrogen, creatinine, glucose, calcium, phosphate, magnesium, AST, ALT, total bilirubin, alkaline phosphatase, total protein, albumin, and uric acid to be performed at screening, for Cycle 1 on Day 1 and Day 8 and for the next three cycles Day 1, 3 and 8 and thereafter once every week and at safety FU visit. During BNT321 monotherapy every cycle on Day 1 and Day 3 and as needed based on investigator's discretion.
- 22. Serum amylase and haptoglobin will be performed on C1D1 and thereafter on Day 1 and Day 3 of every cycle starting at Cycle 2 and at EOT.
- 23. Serum GGT and lipase will be performed on C1D1 and thereafter on Day 1 and Day 3 of every cycle starting at Cycle 2 and at EOT.
- 24. To include color, appearance, glucose, bilirubin, ketone, specific gravity, blood, pH, protein, urobilinogen, nitrite, leukocyte esterase. If warranted by dipstick analysis, microscopic analysis to include RBC, WBC, casts, crystals, epithelial cells, and bacteria. Will be performed at screening and when clinically indicated.
- 25. For POCBPs only.

BioNTech SE

Confidential

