- 14. Is subject to exclusion periods from another investigational trial.
- 15. Are vulnerable individuals as per ICH E6 definition, i.e., individuals whose willingness to participate in a clinical trial may be unduly influenced by the expectation, whether justified or not, of benefits associated with participation, or of a retaliatory response from senior members of a hierarchy in case of refusal to participate.
- 16. Serum CA19-9 > 180 U/mL within 3 weeks of C1D1.
- 17. Incomplete macroscopic tumor removal (R2 resection).

Page 53 of 127 Version: 2.0 Date: 22 JAN 2024

- Significant cardiovascular risk (past medical history of coronary stenting or myocardial infarction within 6 months, or NYHA Class III/IV, heart failure, or concurrent unstable angina) or risk factors for QT prolongation (sustained Grade 3 or higher hypokalemia, history of unstable arrhythmia orfamily history of long QT syndrome).
- 19. Pre-existing neuropathy.
- 20. Homozygous UGT1A1*28 mutation, if testing required by local regulations.
- 21. Inflammatory disease of the colon or rectum, or occlusion or sub-occlusion of the intestine or severe post-operative uncontrolled diarrhea.
- 22. Complete dihydropyrimidine dehydrogenase (DPD) deficiency, if testing required by local regulations.
- 23. Received a live vaccine within 3 weeks prior to the first dose of trial treatment.
- 24. Patients with a contraindication to receiving mFOLFIRINOX.
- 25. Patients with active or latent tuberculosis or history of Mycobacterium tuberculosis infection currently or within the last 2 years.
- 26. Individuals committed to an institution by virtue of an order issued either by the judicial or the administrative authorities.

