8.3.3 Electrocardiograms

Planned time points for ECGs are provided in the SoA (Section 1.3).

If cardiac symptoms occur, during an AE the site should perform an unscheduled ECG to confirm/diagnose the event.

Triplicate/ 12-lead ECG will be recorded as outlined in the SoA using an ECG machine that automatically calculates the ventricular heart rate and measures PR, QRS, QT, and QTcF intervals. Refer to Section 7 for QTc withdrawal criteria and any additional QTc readings that may be necessary.

Triplicate ECG readings should include three individual ECG tracings obtained as closely as possible in succession, but no more than 2 min apart. The full set of triplicates should be completed in less than 4 min.

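### Section 9.5.4 specifies only the investigator's yes/no judgement as the ECG summary; no change from baseline, triplicate rule or outlier categories are planned for QTcF and the other intervals

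*Combined protocol and SAP*

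**What the plan says.** Section 8.3.3 requires 12-lead ECGs on a machine that "automatically calculates the ventricular heart rate and measures PR, QRS, QT, and QTcF intervals". On replication it says: "Triplicate ECG readings should include three individual ECG tracings obtained as closely as possible in succession, but no more than 2 min apart". The ECG footnotes to Tables 1, 2 and 4 in Section 1.3 carry this into Phase I and both Phase II arms: "ECGs are performed as triplicate exams at all study timepoints per Section 8.3.3".

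The ECG paragraph of Section 9.5.4 refers to Section 8.3.3 for the parameters. It then has the investigator judge each ECG as clinically significant or not, and gives one output: "The number and percentage of patients with clinically significant ECG findings will be summarized by treatment group Phase II/cohort Phase I for each visit".

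For vital signs the same section says: "Vital sign parameters at each timepoint and change from baseline to each post-baseline timepoint will be summarized using descriptive summary statistics". Laboratory parameters are treated in the same way, with shift tables in addition.

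At entry the protocol uses QTcF as a number: exclusion criterion 4 sets limits in msec by sex on the average of three ECGs. Criterion 18 excludes patients with "risk factors for QT prolongation".

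**The concern.** Five continuous ECG measures are collected in triplicate, yet the paragraph that governs their analysis turns them into one binary label. A moderate shift in QTcF that no investigator calls significant would not show in that count. Section 6.6.3 states that site personnel know the allocation in Phase II, so a difference between arms in the count could reflect labelling as well as physiology. The usual check on such a label is a table of the measured values and their change, and Section 9.5.4 does not ask for one. What is at stake is the quality of safety reporting, not the efficacy conclusion.

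**Working it through.** The plan gives no figure for the ECG analysis, so there is none to reproduce. The check compares what is collected with what is analysed, then counts the readings that can bear on BNT321.

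**Step 1. Outputs named in Section 9.5.4, by data type**

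| Data | Values by visit | Change from baseline | Abnormality output |
|---|---|---|---|
| Laboratory | yes | yes | CTCAE shift tables; occurrence of clinically significant results |
| Vital signs | yes | yes | occurrence of abnormal results |
| ECG | not named | not named | investigator yes/no count per visit |

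No other part of Section 9 mentions QT, QTc or QTcF, and none says how three tracings become one analysis value.

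**Step 2. Does another stated route fill the gap?**

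- Section 9.5.1 says that continuous variables get n, mean, SD, median, minimum and maximum by group or cohort. This may cover raw interval values. It does not mention change from baseline, replicates or categories.
- Adverse events are tabulated by preferred term and worst grade (Section 9.5.4). Under Section 10.4.1.1 an abnormal ECG is an adverse event only if the investigator considers it clinically significant, and Section 10.4.3 says that findings judged not significant should not be documented as adverse events. This route passes through the same judgement as the yes/no count.

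**Step 3. How many readings inform on BNT321?**

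Inputs: required ECG time points shared by both Phase II arms are screening, C1D1, C2D1, C3D1 and EOT (Tables 2 and 4); 3 tracings per time point (Section 8.3.3); 300 patients randomized 1:1 (Section 9.3); first BNT321 dose on C2D3 under the default schedule (Section 6.3).

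- Screening, C1D1 and C2D1 precede C2D3. C3D1 and EOT follow it, so 2 of the 5 shared time points come after exposure.
- Planned tracings at those two points: 2 x 3 x 300 = 1,800 in both arms, of which 2 x 3 x 150 = 900 are in the combination arm.
- This assumes full attendance and one triplicate per time point. It leaves out the extra same-day recordings at t_max and end of infusion, and the Cycle 13 ECG before BNT321, which has no real counterpart in an arm that stops at Cycle 12.
- With 14-day cycles, C3D1 is 15 - 3 = 12 days after the first BNT321 dose and two days before the second.
- EOT is at completion of 24 cycles in the combination arm (Table 2) and at Week 25 in the control arm (Table 4), unless treatment stops earlier. The two EOT readings are therefore not matched in time.

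The documents give no SD for QTcF, so the precision of a between-arm difference cannot be stated.

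**The case against.** The strongest reply is that Section 9.5 calls itself a summary of the analyses of the most important endpoints and leaves technical detail to a separate SAP. ECG is not an endpoint, and the 9.5.1 rule on continuous variables together with the opening of 9.5.4, which lists ECGs among data to be summarized descriptively, arguably covers QTcF already. This stands in part: raw-value summaries may be intended, and a later SAP could add the rest. But 9.5.4 spells out value and change for laboratory and vital-sign data despite the 9.5.1 rule, and the ECG paragraph neither does so nor defers to the SAP.

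Three stronger readings are tempting, and the documents do not support them.

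- A reader might infer that the yes/no label is the only ECG result and that QTcF will go unreported. Section 9.5.1 and the graded adverse-event tables prevent so flat a statement.
- A reader might count all five shared time points, 5 x 3 x 300 = 4,500 tracings, as lost information on the drug. Three of the five precede BNT321 under the default schedule.
- A reader might infer a known QT risk of BNT321. Table 5 lists cardiac toxicity under mFOLFIRINOX, which both arms receive. Its BNT321 rows cover liver, gastrointestinal and infusion reactions, and the documents report no QT signal for BNT321.

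It is also fair to say that if the interval values are held in the database, labelling can be checked against them later. Such a check would be post hoc unless it is planned now.

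**Conclusion.** The concern holds in a limited form. As written, the plan specifies no ECG change from baseline, no rule for combining the triplicate and no outlier categories, and its two stated ECG routes both depend on unblinded investigator judgement. The gap is in analysis, not collection.

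Its consequence is limited. With about 1,800 planned post-exposure tracings at two shared time points, one of them 12 days after a single dose and the other at different times by arm, the added tables would be descriptive safety reporting with limited information on a BNT321 QT effect. If Day 1 dosing of BNT321 is adopted after SRC review, the overlap of ECGs with exposure changes and this count no longer applies. The conclusion assumes that no separate SAP already contains these tables; no such text was available for this review. The primary DFS analysis does not depend on this point.

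**What to change.** In Section 9.5.4, or in the SAP before the data are reviewed, state that:

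- the mean of each triplicate is the analysis value;
- QTcF, PR, QRS and heart rate are summarized by visit as value and change from baseline, by arm in Phase II and by dose cohort in Phase I, with baseline as Section 9.5.1 defines it;
- patients are counted by prespecified categories of worst post-baseline QTcF and worst increase, with the categories chosen by the sponsor beforehand;
- the investigator's yes/no count stays as a supplement;
- a table note gives the timing of C3D1 and EOT relative to BNT321 in each arm.

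Two neighbouring texts must be reconciled at the same time. Criterion 4 averages three ECGs at least 5 minutes apart, while Section 8.3.3 requires tracings no more than 2 minutes apart, which matters for a screening mean. Section 8.3.3 also points to Section 7 for QTc withdrawal criteria, and Section 7 lists none.

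The cost is wording and a few extra tables. No new visits, patients or recordings are needed, provided that the interval values are entered in the database, which the documents do not say outright.
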